An ACT-Based Physician-Delivered Weight Loss Intervention

Study Protocol

[name], [name], & [name]

July 13, 2016

Study Protocol

The study was approved by the Research Ethics Board (REB-II) at McGill University (Montreal, Canada). Participants provided written informed consent prior to commencing the intervention.

Trial Design

The present study was a two-arm pilot randomized controlled trial conducted from May 7, 2016 to March 7, 2018. Participants were randomized to eight sessions of either an ACT-based intervention aimed at reducing emotional eating or standard care, which involved diet and exercise counselling. All outcomes were assessed at baseline and post-intervention. The present study aimed to recruit 128 participants (64 per condition), similar to the trial protocol outlined by [name] et al. (2014).

Participants

Participants were adults over the age of 18 with overweight or obesity who were seeking treatment for weight loss at a clinic in Toronto, Ontario. Only participants considered to be emotional eaters, as assessed by a score of 3.25 or higher on the Dutch Eating Behavior Questionnaire (DEBQ), were recruited for the study (van Strien, Herman, Anschutz, Engels, & de Weerth, 2012). In addition, participants who did not speak, write, and read in English fluently were excluded from the study, as well as those who were pregnant.

Study Procedures

Participants were recruited upon initial registration at the weight loss clinic. Those who expressed interest to participate were assigned a participant ID number and asked to complete a brief prescreen questionnaire to determine their eligibility based on the criteria described above. Eligible participants were randomly assigned to either the ACT intervention or control condition

based on the ID number they had initially received. Participants completed a battery of questionnaires both baseline and Session 8. Weight was measured every session.

Randomization and Blinding

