Throughout the sessions, physicians formed if-then plans with the patients to specify how to habitually use the ACT techniques to reduce emotional eating in their everyday lives. At the end of each session, participants were given a one-page homework sheet that asked them to monitor their behavior and their use of the ACT techniques during the week. Participants were instructed to bring the homework back with them for the next session so that it could be reviewed with their physician.

Measures

Demographics. At baseline, participants reported basic demographic information including gender, age, English fluency, ethnicity, marital status, educational attainment, employment status, household income, and whether or not they smoked.

Anthropomorphic measures. Weight was measured at each of the eight sessions (primary outcome). Participant body fat percentage was assessed and recorded by their physician at baseline and at completion of the eight sessions (secondary outcome).

Emotional, restrained, and external eating. Participants were pre-screened for emotional eating using the Dutch Eating Behavior Questionnaire (DEBQ; van Strien et al., 1986). The DEBQ is a 33-item questionnaire that assesses three dimensions of eating behaviors: emotional eating (primary outcome), restrained eating (secondary outcome), and external eating (secondary outcome). The emotional eating subscale assesses the reported desire to eat under specific negative emotional conditions such as stress, anxiety, and depression. The DEBQ has high internal consistency and factorial validity (van Strien et al., 1986). The DEBQ was administered again post-intervention.

Distress tolerance. The Distress Tolerance Scale (DTS; Simons & Gaher, 2005), a brief self-report questionnaire that assesses one's ability to tolerate distressing emotions, was completed at baseline and post-intervention (secondary outcome). The scale is made up of items that assess the dimensions of distress tolerance, absorption, appraisal, and regulation. The DTS has high reliability and high discriminant, convergent, and criterion validity (Leyro, Bernstein, Vujanovic, McLeish, & Zvolensky, 2011; Simons & Gaher, 2005).

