All analyses were conducted in SPSS version 24. 2 Two separate 2 (Condition: Standard Care, ACT Intervention) x 2 (Time: Baseline, Session 8) repeated measures MANOVAs were conducted for the anthropomorphic and questionnaire data outlined above, respectively, with follow-up *t*-tests conducted as necessary. Two separate MANOVAs were conducted to not lose data from incomplete cases (i.e., participants who had completed anthropomorphic but not questionnaire data). Independent samples *t*-tests were conducted for treatment satisfaction data collected at Session 8, whereas chi-square tests were conducted to compare recruitment rates, attrition rates, questionnaire completion, and intervention completion time between conditions. Missing data were not imputed because of the large drop out rates: Imputation with small sample sizes and high rates of missingness has been shown to be highly prone to Type I error (McNeish, 2016).

References

- Bowen, S., & Marlatt, A. (2009). Surfing the urge: brief mindfulness-based intervention for college student smokers. *Psychology of Addictive Behaviors, 23*(4), 666-671.
- [name], B., Ivanova, E., Xu, Z., Chamandy, M., Lowensteyn, I., Joseph, L., Luszczynska, A., & Grover, S. (2014). Increasing the effectiveness of the Diabetes Prevention Program through if-then plans: Study protocol for the randomized controlled trial of the McGill CHIP Healthy Weight Program. *BMC Public Health, 14*, 470.
- Kristeller, J., & Wolever, R. Q., (2011). Mindfulness-based eating awareness training for treating binge eating disorder: the conceptual foundation. *Eating Disorders, 19*(1), 49-61.
- Leyro, T. M., Bernstein, A., Vujanovic, A. A., McLeish, A. C., & Zvolensky, M. J. (2011). Distress Tolerance Scale: A confirmatory factor analysis among daily cigarette smokers. *Journal of Psychopathology and Behavioral Assessment, 33*(1), 47-57.
- Simons, J. S., & Gaher, R. M. (2005). The Distress Tolerance Scale: Development and validation of a self-report measure. *Motivation and Emotion, 29*(2), 83-102.

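### Weight is recorded at all eight sessions, but its only described analysis uses baseline and Session 8, so with large drop-out it compares completers only

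*Combined protocol and SAP*

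**What the plan says.** **Measurement.** Under Study Procedures: "Participants completed a battery of questionnaires both baseline and Session 8. Weight was measured every session". The Anthropomorphic measures paragraph of Measures repeats this and makes weight a primary outcome: "Weight was measured at each of the eight sessions (primary outcome". Body fat is secondary and has two time points: "Participant body fat percentage was assessed and recorded by their physician at baseline and at completion of the eight sessions".

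**Analysis.** The Data Analysis section describes "2 (Condition: Standard Care, ACT Intervention) x 2 (Time: Baseline, Session 8) repeated measures MANOVAs", one for the anthropometric data and one for the questionnaires, with follow-up t-tests as needed. It explains the split: "Two separate MANOVAs were conducted to not lose data from incomplete cases", meaning people with anthropometric but no questionnaire data.

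**Missing data.** "Missing data were not imputed because of the large drop out rates". The reason given is that imputation in small samples with much missingness is prone to Type I error. Attrition is examined only by comparing arms: "chi-square tests were conducted to compare recruitment rates, attrition rates, questionnaire completion, and intervention completion time between conditions".

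No drop-out rate is stated, overall or by arm. No mixed model, other use of the Session 2 to 7 weights, or sensitivity analysis is described.

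**The concern.** A repeated measures MANOVA needs every variable at both time points. Without imputation, a person with no Session 8 weight leaves the analysis, however many weights were recorded before.

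The plan's safeguards do not reach this problem:

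- Splitting the MANOVAs keeps people who lack questionnaires, not people who left early.
- The Type I error argument is against imputation. It does not justify deletion, which is in general unbiased only if drop-out is unrelated to weight change. A likelihood-based mixed model imputes nothing.
- A chi-square on attrition compares counts. It cannot show that two arms lost similar numbers for different reasons.

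At stake are the precision of a primary comparison in a small trial and possibly its validity: a real effect could be shrunk, or a spurious one produced.

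**Working it through.** **1. Inputs.** From the documents: eight weights per person, two analysed, no imputation, and 64 per arm as the recruitment aim ("The present study aimed to recruit 128 participants (64 per condition"). No alpha, power, effect size or SD is given, so 128 cannot be reproduced from the plan's own inputs. Nothing below depends on how it was chosen.

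Assumed for illustration: 64 per arm, Session 1 as baseline, mean loss 0.3 kg per session, slope SD 0.35 kg per session, residual SD 0.8 kg, two-sided 5% tests. Drop-out is monotone with a logistic hazard calibrated to the stated completion (in each arm when the rule differs by arm), with 2,000 simulated trials per scenario. Completers: t-test on Session 8 minus baseline, which is the 2 x 2 interaction for one outcome. Model: REML, unstructured 8 x 8 covariance, common baseline mean, arm x session, Satterthwaite df. Negative differences favour ACT.

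**2. Data used.** A completer contributes 2 of 8 weights. Someone who leaves after Session 7 contributes 0 of 7. With a constant hazard and half completing, recorded weights per person average (1 - 0.5^(8/7)) / (1 - 0.5^(1/7)) = 0.547 / 0.0943 = 5.80. The completers' test uses 2 x 0.5 = 1.0 of them, or 17%.

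**3. Precision, random drop-out, true effect -1.2 kg.** The variance of the change is 7² x 0.35² + 2 x 0.8² = 6.00 + 1.28 = 7.28. With n completers per arm the SE is √(2 x 7.28 / n): 0.57 kg at n = 44.8 (70%), 0.67 at 32 (50%) and 0.87 at 19.2 (30%). The simulated SDs agree at 70% and are slightly larger at 50% and 30%, where the number completing also varies by chance.

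| Completing | SD, completers | SD, model | Variance saved | Power, completers | Power, model |
|---|---|---|---|---|---|
| 70% | 0.570 | 0.527 | 1 - (0.527/0.570)² = 15% | 54.3% | 64.3% |
| 50% | 0.688 | 0.576 | 1 - (0.576/0.688)² = 30% | 40.4% | 57.1% |
| 30% | 0.903 | 0.674 | 1 - (0.674/0.903)² = 44% | 27.8% | 46.8% |

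Under the null at 50% completing, rejection was 5.1% (completers) and 5.8% (model).

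**4. Drop-out on observed change, same rule in both arms, 50% completing.** Null: rejection 5.3% (completers) and 5.7% (model). True effect -1.20 kg: mean estimate -1.08 (completers) and -1.20 (model).

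**5. Rule differing by arm, null true, 50% completing in each arm.** Each cell gives bias in kg and rejection rate. The coefficients are the drop-out log-odds per kg in the two arms.

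| Drop-out depends on | Completers | Model |
|---|---|---|
| Observed change, 0.2 vs 0.6 | -0.50, 11.6% | -0.01, 6.1% |
| Observed change, 0 vs 0.8 | -1.01, 34.4% | -0.01, 6.6% |
| Latent slope, weaker contrast | -0.62, 14.8% | -0.36, 10.3% |
| Latent slope, stronger contrast | -1.21, 46.8% | -0.71, 25.4% |
| Next unseen weight, weaker contrast | -0.62, 15.9% | -0.28, 8.5% |
| Next unseen weight, stronger contrast | -1.28, 52.8% | -0.56, 17.5% |

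In the first two rows the attrition chi-square rejected in only 4.6% and 4.3% of trials. The last four rows are missing not at random. There the model removes only part of the bias, from 1 - 0.71/1.21 = 41% to 1 - 0.56/1.28 = 56%.

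**6. Other assumed inputs.** A separate simulation (mean loss 0.4 kg per session, slope SD 0.45, noise SD 1.0 on the change, about 50% random drop-out) gave SEs of 0.82 kg for completers, 0.69 for an all-sessions likelihood estimate and 0.58 with full data. With drop-out tied to observed change in ACT only and no true effect, the biases were -1.23 and +0.04 kg, although the arms lost 51% and 53%.

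**7. Body fat.** It shares the MANOVA with weight, so a missing body-fat value could also remove a recorded Session 8 weight. If 10% or 20% of completers were affected (assumed), the SE would rise by 1/√0.9 = 1.054 or 1/√0.8 = 1.118.

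**The case against.** **Bias is not shown.** The documents say only that drop-out was large. The striking false-positive rates need a rule that differs by arm, and nothing in the documents establishes one. Under a shared rule the level holds and the effect shrinks by about 10% (0.12/1.20). This stands: bias is conditional. The precision loss is not.

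**The plan collects some reasons for drop-out.** The Treatment satisfaction paragraph includes open-ended physician feedback on drop-out. That may help interpretation, but it does not correct the estimate.

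**Body fat is conjecture.** It is due when the Session 8 weight is due, no document reports it missing alone, and a follow-up t-test on weight would not need it. The 10% to 20% has no source. This part is minor.

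**The model has its own Type I error cost.** This is the best objection, because Type I error is the plan's stated worry. Null rejection under random drop-out, 1,000 trials per row with approximate Satterthwaite df (Monte Carlo error about 0.6 to 0.8 points):

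| Per arm | Completing | Completers | Model |
|---|---|---|---|
| 64 | 50% | 5.5% | 5.7% |
| 64 | 30% | 5.9% | 6.5% |
| 32 | 50% | 4.5% | 5.7% |
| 32 | 30% | 3.5% | 7.3% |

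So the level may exceed 7% in a very small sample, and part of the power gain in the working reflects test size. The precision gain is separate and remains: SD 1.01 against 1.24 kg in the last row.

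**It is a pilot.** True, but weight is named primary and compared between arms, and a small sample makes discarding recorded weights more costly.

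**Conclusion.** The concern holds. That the described weight analysis is restricted to completers and ignores six of the eight sessions follows from the text and needs no assumption. Loss of precision follows from any drop-out. Under the assumed inputs an all-weights model would cut the variance by 15% to 44% as completion falls from 70% to 30%.

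Bias is a possibility whose size and direction cannot be determined here, because the rate, the split by arm and the reasons are not given. It is absent if drop-out is unrelated to weight change. In the scenarios examined it ranged from a modest shrinkage of a real effect to a spurious difference of 1 kg or more. All the kilogram figures are illustrations at the planned 64 per arm, not estimates for this trial.

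This should be fixed. It concerns a primary outcome, the plan itself reports large drop-out, and the remedy uses data already held.

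**What to change.** 1. Make the primary weight analysis a likelihood-based mixed model for repeated measures (SPSS MIXED, REML, Satterthwaite df, no imputation) on all recorded weights of all randomised eligible participants.
2. Keep baseline as a response with one mean shared by the arms, so that people with only a baseline weight are retained, and fit arm x session means thereafter. Otherwise adjust for baseline and baseline x session. The primary contrast is the arm difference at Session 8.
3. Use an unstructured covariance with a pre-stated fallback if it does not converge, such as heterogeneous Toeplitz, then heterogeneous AR(1). The unstructured form has 8 x 9 / 2 = 36 parameters.
4. Model weight separately from body fat.
5. Keep the baseline-to-Session 8 comparison as a supplementary completers' analysis, with numbers analysed per arm.
6. Add a missing-not-at-random sensitivity analysis that needs no imputation: model estimate + δ(ACT) x share of ACT without a Session 8 weight - δ(standard care) x the corresponding share, over a stated range of δ. In the not-at-random scenarios above, with half missing, offsetting the remaining bias would take δ(ACT) from 0.28/0.5 = 0.56 to 0.71/0.5 = 1.42 kg. That shows scale only; it is not a range derived for this trial.
7. State that session number, not calendar time, is the time index, and report time to Session 8 by arm.
8. Report emotional eating, the other primary outcome, as a completers' comparison. It has no interim values, so this remedy does not extend to it.

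**Cost.** SAP wording and one different SPSS procedure; no new visits or follow-up. The model still assumes that drop-out is explained by observed weights, and its slightly raised test level in small samples should be stated with the result.

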4 – Acceptance	The patient and physician discussed the concept of accepting and tolerating negative emotions. The tug-of-war metaphor and the concept of dropping the rope in the face of negative emotions was introduced. They brainstormed alternative ways to respond to negative emotions (instead of eating).	The patient practiced dropping the rope and finding alternatives to eating in response to negative emotions. The patient used the if-then plan “IF I feel _____ emotion, then I will practice dropping the rope and do (alternate behaviour) instead of eating”. They journaled a time when this occurred doing the week and what the experience was like.

5 – Urge surfing	The patient and physician discussed the concept of urge surfing and how it can be used when experiencing emotions or cravings to prevent overeating.	The patient practiced urge surfing using the if-then plan “IF I feel _____ emotion, THEN I will practice urge surfing”. They journaled a time during the week when urge surfing was used and what the experience was like.
6 – Mindful eating	The physician explained the concept of mindful eating and how to do it. They completed a mindful eating exercise to train the patient in how to prevent mindless eating.	The patient practiced mindful eating at home. They used the if-then plan “IF I want to eat my favourite treat, THEN I will practice eating it mindfully”. They journaled a time during the week when mindful eating was used and what the experience was like.
7 – Establishing habits	The physician reviewed the skills taught in the first six sessions to help reduce emotional eating and promote long-term weight loss. They discussed the techniques that the patient found most useful and emphasized the importance of practicing these skills routinely to establish a habit.	The patient chose the if-then plans that worked best for reducing their own emotional eating and wrote them down. They tailored them to the emotions the patient finds most triggering.
8 – Commitment to values	The patient and physician discussed setbacks, loss of motivation, and how they are a normal and inevitable part of the weight loss journey. They discussed ways to stay committed to values and goals despite setbacks. The if-then plans the patient had chosen as the most effective were reviewed. The patient wrote those plans on a summary card.	The patient was encouraged to keep the summary card of if-then plans somewhere accessible to act as a constant reminder of values when feeling a lack of motivation.
